**Placebo-controlled randomised trial of tecovirimat
in non-hospitalised Mpox patients (PLATINUM)**

Background: Mpox is an acute febrile rash illness caused by the monkeypox virus. Since its first human identification in 1970, the majority of cases have been reported from Africa. Historically, there have been sporadic travel associated cases in countries outside of Africa, with very limited onward transmission.

Following notification from the United Kingdom to WHO on the 15th of May 2022, of two confirmed and one probable case of mpox, person-to-person transmission of mpox has been observed in multiple countries outside of Africa.

Several investigational antivirals demonstrate activity against monkeypox virus in vitro and in animal models, but none has been evaluated in a clinical trial. The most promising is tecovirimat, which is an oral anti-viral drug developed by SIGA Technologies, Inc. and approved by the US Food and Drug Administration (FDA) for the treatment of smallpox and by the European Medicines Agency (EMA) and Medicines and Healthcare products Regulatory Agency (MHRA), under an exceptional circumstances rule, for the treatment of smallpox, cowpox and mpox.

Eligibility and randomisation: This protocol describes a double-blind, placebo-controlled, randomised trial among non-hospitalised adults and children with laboratory-confirmed mpox. Patients will be identified following clinical assessment and laboratory confirmation of mpox infection as part of usual clinical care. All eligible and consenting patients will be randomly allocated (1:1) to receive tecovirimat or matching placebo for 14 days, each to be given in addition to the usual standard of care.

Study endpoints: The primary clinical efficacy endpoint is the time to resolution of active lesions. Secondary efficacy endpoints are time to complete lesion resolution, and the time to negative cultures for monkeypox virus in throat and lesion swabs. Safety data will also be collected. For the main analyses, follow-up will be censored at 28 days after randomisation. Additional information on longer term outcomes may be collected through review of medical records or linkage to medical databases (such as those managed by NHS Digital and other health care organisations). Additional assessments may be conducted following the end of the main assessment period of the study (28 days) to assess complete resolution of mpox symptoms.

Safety: All adverse events, and reasons for stopping study treatment will be recorded and will be reviewed by medical staff at the Central Coordinating Office. Suspected Unexpected Serious Adverse Reactions (SUSARs) to study medication (e.g., Stevens-Johnson syndrome, anaphylaxis, aplastic anaemia, etc.) will be reported in an expedited fashion.

Data collection: To facilitate patient isolation and infection control, and participation by clinicians and patients, data collection and all other trial procedures are streamlined and focused on those aspects critical to participant safety and the reliability of the study results. Informed consent, randomisation and follow up will be conducted remotely by telephone call or video call and data will be recorded by electronic methods by participants and trial staff.

Numbers to be randomised: The rates of clinical and microbiological resolution are uncertain for mpox in general, and in particular for the current epidemiological context.

Sample size estimates using data on the natural history of clade 1 (Congo Basin clade) mpox indicate that randomisation of 500 individuals would provide at least 85% power and a two-sided α of 0.05 to detect a 40% improvement in the rate of lesion resolution at day 28 (account for one interim analysis and approximately 10% losses to follow-up). Monitoring of blinded event rates will be used to re-estimate sample size requirements as data from the trial accrue.

Study organisation: The study is led by researchers at the University of Oxford (the regulatory trial sponsor) and includes experts in infectious disease at the Pandemic Sciences Institute and experienced clinical trialists applying methods established in the RECOVERY and PANORAMIC trials of treatments for COVID-19. Chelsea and Westminster Hospitals NHS Trust is providing sexual health expertise. The University of Liverpool is providing laboratory expertise. The study is coordinated by the Clinical Trial Service Unit in the Nuffield Department of Population Health.

To enquire about the trial, contact the PLATINUM Central Coordinating Office

PLATINUM Central Coordinating Office:
Nuffield Department of Population Health
[name]
[name]
[name]
[name]
United Kingdom

Tel: TBC
Email: TBC

Website: TBC

Table of contents

1 BACKGROUND AND RATIONALE 5

1.1 MPOX 5

1.2 TREATMENT OPTIONS..... 5

1.3 DESIGN CONSIDERATIONS 6

2 STUDY DESIGN..... 8

2.1 STUDY AIMS 8

2.2 ELIGIBILITY..... 8

1 BACKGROUND AND RATIONALE

1.1 Mpox

Mpox is an acute febrile rash illness caused by the monkeypox virus. The clinical features of human mpox closely resemble those of smallpox, although mpox is typically milder than smallpox.⁽¹⁾

Two distinct clades of mpox have previously been characterized: Clade 1 (Congo Basin) and Clade 2 (West African). Clade 2 has a reported mortality of approximately 1-4%. Clade 1 is associated with higher mortality (up to 10%) and seems to transmit more frequently between humans.⁽²⁾ After a 5 to 21-day incubation period, a prodromal illness with fever, malaise, and painful swollen lymph nodes is observed in most patients. The prodromal period generally lasts 1–3 days before the occurrence of the typical vesiculo-pustular rash, which lasts 2 to 4 weeks. Skin lesions are characteristic of the disease with uniform progression from macules to papules, vesicles, pustules, umbilication, crusting and finally desquamation. In addition to skin lesions, extracutaneous manifestations, such as secondary skin and/or soft-tissue infection (19% of cases), pneumonitis (12%), ocular complications (4%–5%), and encephalitis (<1%) can be observed in patients infected with mpox. Death, when it occurs, generally occurs during the second week of the lesional stage of the disease. Subclinical infection and asymptomatic cases have also been reported with an estimated rate of approximately 30%.⁽³⁾

Mpox case numbers have been increasing in Central and West Africa over recent years, possibly due to waning of population immunity derived from the smallpox eradication program.⁽⁴⁻⁷⁾ Historically, there have been sporadic imported cases to the UK with limited onward transmission. ^(8, 9)

Following notification from the United Kingdom to WHO on the 15th of May 2022, of two confirmed and one probable case of mpox, many countries are reporting a growing number of mpox cases without a travel history, indicating person-to-person transmission of mpox. The viruses associated with these cases are most closely related to clade 2 but have some genetic differences and has been tentatively named Clade 3.

The epidemiology and clinical characteristics of the current outbreak are atypical. From 1 January to 22 June 2022, 3413 laboratory confirmed cases and one death have been reported to WHO from 50 countries/territories in five WHO Regions. The majority of laboratory confirmed cases (2933/3413; 86%) were reported from the WHO European Region. As of 11 July, there were 1,735 confirmed cases in the UK, of which 1,660 are in England. The majority of the cases identified to date have been among men who have sexual activity with men (<https://www.gov.uk/government/publications/monkeypox-outbreak-technical-briefings/investigation-into-monkeypox-outbreak-in-england-technical-briefing-4>). However, there have also been cases in other groups. There has been a preponderance of genital, perianal and mucosal lesions, rather than the centrifugal rash classically described for mpox. Some of the lesions have persisted for a long period and some patients have required hospitalisation for pain management or treatment of secondary skin infections.

1.2 Treatment Options

To date, most of the patients affected by mpox receive only supportive and symptomatic care as standard treatment. However, several investigational antivirals demonstrate activity

against monkeypox virus in vitro and in animal models, but none has been evaluated in a clinical trial. The most promising is tecovirimat, which is an oral anti-viral drug developed by SIGA Technologies, Inc. (10-18) In 2018, the FDA granted SIGA Technologies, Inc. approval of tecovirimat for the treatment of human smallpox disease in adults and paediatric patients weighing at least 13 kg (for the oral formulation) under the Animal Rule (SIGA NDA 208627 and SIGA IND 69019). (19) In June 2022, the MHRA granted marketing authorisation (under an 'exceptional circumstances' rule) for tecovirimat for the treatment of mpox and other orthopoxvirus diseases including vaccinia complications in adults and children of at least 13 kg body weight. (20)

1.3 Design Considerations

The PLATINUM trial protocol describes an overarching trial design to provide reliable evidence on the efficacy of tecovirimat for laboratory-confirmed mpox in patients presenting to healthcare services and managed as outpatients. Since patients hospitalised for complications of mpox treatment may be prescribed tecovirimat for clinical indications, the trial is restricted to outpatients.

It is anticipated that such patients will be seen initially in healthcare facilities where the provisional diagnosis will be made and lesion and/or throat swabs taken for measurement of monkeypox virus DNA by PCR in biosecure clinical laboratories run or authorised by the Health Security Agency (HSA). Thus the identification of eligible cases is considered to be part of routine NHS clinical care.

The protocol is suitable for a wide range of settings, allowing a broad range of patients to be enrolled, potentially in large numbers. The trial has been designed so that it could accommodate patients who may be assessed in a variety of medical settings (e.g. genitourinary medicine clinics, accident & emergency departments, primary care, or through public health services). The approach to recruitment is strongly informed by the experience of the PRINCIPLE and PANORAMIC trials of treatments for COVID-19 and is designed to be readily integrated into standard clinical and public health workflows for this disease.

Confirmed cases may be geographically widely distributed and the settings in which cases are diagnosed may change over time. To recruit patients diagnosed through multiple clinical and public health sites and settings without the need for numerous clinical trial agreements, the trial will be conducted as a "remote" trial without research sites or participant identification centres. In accordance with Health Research Authority (HRA) guidance*, research participants will be identified through normal clinical activity (e.g. a routine clinic) and referred to the research study in order to gain access to the clinical intervention. Trial activities will be being overseen by the Chief Investigator who will delegate trial duties to other appropriately trained and qualified staff and formally record such delegation.

At the time of starting this trial, most cases are young or middle aged adults who do not require hospital care and will be managed at home but who do require strict isolation for infection control purposes. Therefore, the protocol is designed to be implemented through a mixture of patient self-assessment, video or telephone call assessment by trial team members, and self-swabbing. Although the vast majority of patients are adults, the protocol includes a provision for the recruitment of children weighing ≥ 13 kg.

* <https://www.myresearchproject.org.uk/help/hlpsitespecific.aspx#PIC>

Since the assessment of symptoms and lesions status, and compliance with trial procedures may be influenced by knowledge of treatment allocation, a placebo controlled trial design (rather than open label) is necessary in order to reliably assess the effects of the treatment. Accurate quantification of any clinical benefit or impact on infectiousness is particularly important for a drug such as tecovirimat, where availability and cost may limit the extent to which its use is recommended, especially in people with mild disease.

.

2 STUDY DESIGN

2.1 Study aims

The PLATINUM trial aims to provide reliable evidence about the efficacy and safety of oral tecovirimat in the treatment of acute mpox infection among patients who do not require admission to hospital. The trial will evaluate whether a two-week course of tecovirimat increases the rate of resolution of mpox skin and mucosal lesions, and/or increases the rate of viral clearance as defined by viral culture of throat and lesion swabs. PLATINUM will use a remote design, combining online forms for self-assessment of lesion resolution and calls from staff at the Central Coordinating Office. Couriers will deliver tecovirimat or matching placebo to participants who are self-isolating because of their infection, and will also collect self-taken follow-up swabs for analysis at a central laboratory. The trial aims to recruit 500 participants with confirmed mpox, who will followed-up for 28 days following trial entry.

2.2 Eligibility

Patients are *eligible* for the study if **all** of the following are true:

- (i) Laboratory-confirmed mpox infection
- (ii) The presence of active skin or mucosal lesion(s)*
- (iii) Patient is appropriate to be managed without hospitalisation
- (iv) Women with reproductive potential[†] are willing to use effective contraception[‡] from the time of enrolment through study day 28.

Patients are to be *excluded* if **any** of the following are true:

- (i) Weight <13 kg (children weighing more than this are eligible)
- (ii) Planned use of contraindicated treatment (see section 2.5.5) during study period
- (iii) Current or past use of tecovirimat
- (iv) Lack of capacity to provide informed consent
- (v) The referring doctor considers there to be a definite indication for tecovirimat
- (vi) Hypersensitivity to tecovirimat or any excipients in the study treatment
- (vii) Current pregnancy or breastfeeding
- (viii) Clinically determined severe renal impairment i.e., under the care of a nephrologist
- (ix) Clinically determined severe hepatic impairment i.e. under the care of a hepatologist
- (x) Diagnosis of epilepsy

Other considerations:

- (i) Patients who have received an orthopoxvirus vaccination may be included.
- (ii) Limited safety trials including an elderly population (up to the age of 79 years) suggest no clinically important effects of age on the safety of tecovirimat. Therefore, there is no upper age limit on participation in the trial.[\(18\)](#)

* An active lesion is a skin lesion that is not scabbed or desquamated or a mucosal lesion that has not healed.

† Female reproductive potential is defined as the time following menarche until becoming post-menopausal, unless permanently sterile. Permanent sterilisation methods include hysterectomy, bilateral salpingectomy and bilateral oophorectomy.

‡ Acceptable methods of effective contraception include the following: intrauterine devices; progestogen-only injections, pill or implant; combined hormonal contraception (pill, patch or vaginal ring); male or female condom; diaphragm or cervical cap with a spermicide.

- (iii) There is no upper time limit for days since symptom onset. However, the Trial Steering Committee will monitor this aspect of recruitment and may introduce an upper time limit to ensure that a substantial proportion of participants are enrolled early in the disease (when the anti-viral effects of tecovirimat are most likely to be greater).

2.2.1 Pregnancy and breastfeeding

Background: No adequate and well-controlled studies of tecovirimat in pregnant women have been conducted. Therefore, there are no human data to establish the presence or absence of tecovirimat-associated benefit or risk in pregnancy. In animal reproduction studies, no developmental toxicity was observed in mice during the period of organogenesis at tecovirimat exposures (area under the curve) up to 23 times higher than human exposure at the recommended human dose. In rabbits, no developmental toxicity was observed during organogenesis at tecovirimat exposures less than human exposures at the recommended human dose. In a mouse pre-/post-natal development study, no toxicities were observed at maternal tecovirimat exposures up to 24 times higher than human exposure at the recommended human dose.

Similarly, there are no data to assess the effect on milk production, the presence of the drug in human milk, and/or the effects on the breastfed child. When administered to lactating mice, tecovirimat was present in the milk.⁽¹⁹⁾ The developmental and health benefits of breastfeeding should be weighed against the mother's clinical need for tecovirimat and any potential adverse effects on the breastfed child from tecovirimat or from the underlying maternal condition.

Pregnant women may be at risk for more severe disease and possible congenital mpox disease.⁽²¹⁾ It remains unclear what the risk of severe mpox is in breastfeeding women. Pregnant women will be excluded from this trial. Non-pregnant women with reproductive potential must agree to use effective means of contraception when engaging in sexual activities that can result in pregnancy, from the time of enrolment through study day 28. Acceptable methods of contraception include the following: intrauterine devices; progestogen-only injections, pill or implant; combined hormonal contraception (pill, patch or vaginal ring); male or female condom; diaphragm or cervical cap with a spermicide. If a woman becomes pregnant during the trial treatment period, she will discontinue the study drug.

Women who are breastfeeding will need to stop breastfeeding to be eligible for enrolment. The benefits and risks of this decision will be made between the patients' treating clinician and the patient.

2.2.2 Immunocompromised Patients

Background: The safety of tecovirimat in immunocompromised individuals has not yet been established. No clinical studies of tecovirimat in immunocompromised patients have been performed. Studies in immunocompromised animal models demonstrated a potential for reduced efficacy, but no increased safety concern.⁽²⁵⁾

Given that immunocompromised patients may be at risk for more severe disease or death, the potential benefits of receiving tecovirimat may outweigh potential risks. Therefore, immunocompromised patients will be eligible for enrolment.

2.2.3 Older adults

Background: A randomized, double-blind, safety trial involving healthy volunteers had a median age of tecovirimat recipients (n=359) of 38 years, an age range of 18 to 79 years and 10% of participants were aged 65 years or older.⁽¹⁸⁾ This study did not identify any age-related safety concerns and the EU SmPC for tecovirimat does not have an upper age for use in the clinic.

Given the lack of any safety concerns in healthy adults up to the age of 79 years and the possibility (but unknown) risk for more severe disease in older adults, there is no upper age limit for inclusion in the trial.

2.2.4 Children and Adolescents

Background: The safety of tecovirimat in children and adolescents below 18 years of age has not yet been established. Paediatric subjects have not been studied in clinical trials with tecovirimat. Safety data are available for young adults and these show no clinically important effects of age on the safety of tecovirimat.⁽¹⁸⁾

Historically, mpox has been a disease that affects children as well as adults. Given that paediatric patients commonly experience more severe disease than adults that routinely requires intensive care, the potential benefits of receiving tecovirimat may outweigh potential risks. Therefore, children weighing ≥ 13 kg will be eligible for enrolment.

2.2.5 Contraindications due to other treatments.

The Summary of Product Characteristics provides cautions for tecovirimat use with several concomitant medications. Patients taking these medications during the study period will not be eligible for enrolment. Discussions regarding whether it is appropriate to temporarily discontinue or replace one of these medications for an alternative will need to occur (and be documented) with their usual treating clinician before a patient is considered eligible for enrolment.

- Bupropion
- Repaglinide
- Voriconazole
- Rilpivirine
- Maraviroc
- Midazolam
- Atorvastatin
- Tacrolimus
- Methadone
- Flurbiprofen
- Phosphodiesterase type 5 inhibitors (sildenafil, tadalafil, vardenafil)
- Darunavir
- Proton pump inhibitors (lansoprazole, omeprazole, rabeprazole)

2.2.6 Comorbidities

Use in people with epilepsy: The potential for tecovirimat to lower seizure threshold is unknown and so persons with a diagnosis of epilepsy will not be eligible for enrolment.

Renal and hepatic impairment: There is limited clinical data regarding tecovirimat use in patients with severe renal or hepatic impairment, and there is a risk of higher unbound drug and metabolites. Biological sampling for drug plasma concentrations cannot be undertaken in this trial and so patients with

- a) clinically determined severe renal impairment (defined as being under the treatment of a nephrologist); or
- b) clinically determined severe hepatic impairment (defined as being under the care of a hepatologist)

will not be eligible for enrolment.

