2.8 Data and safety monitoring

The study will collect information on:

- (i) **Serious Adverse Events (SAE):** A SAE is any adverse event that:
 - results in death
 - is life-threatening*
 - requires inpatient hospitalisation or prolongation of existing hospitalisation
 - results in persistent or significant disability/incapacity
 - consists of a congenital anomaly or birth defect.

The MHRA SmPC will be the source of Reference Safety information (RSI).

- (ii) **Non-serious Adverse Events (NSAE):** This includes any new symptoms reported by the participant. Participants will be specifically asked about AEs of special interest, including headache, sore eyes, cough, shortness of breath, nausea, vomiting, diarrhoea, muscle aches, joint pain.

rm "life-threatening" in the definition of "serious" refers to an event in which the participant was at risk of death at the time of the event; it does not refer to an event which hypothetically might have caused death if it were more severe

(iii) **Reasons for prematurely stopping allocated study treatment.**

These will be ascertained from the weekly review calls with the participant by a study clinician (up to day 28), and spontaneous reports from healthcare professionals caring for the participant. In addition, participants (and their parents or carers if under 16) will be provided with a dedicated 24-hour phone support line for any trial-related queries, and with a wallet card containing details of the trial that they should carry with them during the 28 day follow-up period. These safety outcomes will be collected up to day 28 (i.e. 14 days after the completion of study treatment). Study staff that become aware of a potential SAE will report this within 24 hours to the Chief Investigator or their designee.

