The safety of tecovirimat was evaluated in 359 healthy adult subjects ages 18-79 years in a Phase 3 clinical trial. The most frequently reported adverse reactions (occurring in at least 5% of subjects) were headache and nausea. Abdominal pain and vomiting each occurred in 2% of subjects. A total of 6 subjects discontinued drug due to mild adverse reactions and one abnormal EEG change. Additional details on less common adverse reactions and the adverse reactions that led to drug discontinuation are found in the TPOXX prescribing information.(2)

Tecovirimat is a weak inducer of cytochrome P450 (CYP)3A and a weak inhibitor of CYP2C8 and CYP2C19. However, the effects are not expected to be clinically relevant for most substrates of those enzymes based on the magnitude of interactions and a maximum 14-day duration of tecovirimat administration, with the exception of repaglinide and midazolam as follows.

Co-administration of repaglinide and tecovirimat may cause mild to moderate hypoglycemia. In a drug interaction study, 10 of 30 healthy subjects experienced mild (6 subjects) or moderate (4 subjects) hypoglycemia following co-administration of repaglinide (2 mg) and tecovirimat. Symptoms resolved in all subjects after intake of food and/or oral glucose.

Co-administration of midazolam and tecovirimat may reduce the effectiveness of midazolam. Effectiveness of midazolam should be monitored when administering tecovirimat with midazolam.

Refer to the tecovirimat prescribing information for additional information on drug interactions.[\(2\)](#)

Formulation, Appearance, Packaging, and Labelling

Tecovirimat is available as immediate-release capsules containing tecovirimat monohydrate equivalent to 200 mg of tecovirimat for oral administration. The capsules are imprinted in white ink with “SIGA” followed by the SIGA logo followed by “®” on an orange body, and a black cap imprinted in white ink with “ST-246®.” The capsules include the following inactive ingredients: colloidal silicon dioxide, croscarmellose sodium, hydroxypropyl methyl cellulose, lactose monohydrate, magnesium stearate, microcrystalline cellulose, and sodium lauryl sulfate. The capsule shell is composed of gelatin, FD&C blue #1, FD&C red #3, FD&C yellow #6, and titanium dioxide.

Tecovirimat capsules are supplied in 75-cc high-density polyethylene bottles fitted with a heat induction seal and child-resistant screw cap closure system.

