2.4.2 Exclusion criteria

Patients are to be *excluded* if **any** of the following are true:

- (i) Weight <13 kg (children weighing more than this are eligible)
- (ii) Planned use of contraindicated treatment (see protocol section 2.2.5) during study period
- (iii) Current or past use of tecovirimat
- (iv) Lack of capacity to provide informed consent
- (v) The referring doctor considers there to be a definite indication for tecovirimat
- (vi) Hypersensitivity to tecovirimat or any excipients in the study treatment
- (vii) Current pregnancy or breastfeeding
- (viii) Clinically determined severe renal impairment, i.e. under the care of a nephrologist
- (ix) Clinically determined severe hepatic impairment, i.e. under the care of a hepatologist
- (x) Diagnosis of epilepsy

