2.6 Outcomes

2.6.1 *Primary outcome*

Time (in days) to active lesion resolution, defined as the first day on which all skin lesions are scabbed or desquamated (and mucosal lesions healed), up to 28 days after randomisation.

2.6.2 *Secondary clinical outcomes*

- (i) Time (in days) to complete lesion resolution, defined as the first day on which all lesions are completely resolved (all scabs dropped off and intact skin remains underneath, and mucosal lesions healed), up to 28 days after randomisation
- (ii) Time to negative throat swab viral culture, defined as time to consistently negative culture for monkeypox virus on throat swab at Days 7, 14, 21, and 28
- (iii) Time to negative skin or mucosa swab viral culture, defined as time to consistently negative culture for monkeypox virus on swab of most recent active skin or mucosa lesion at Days 7, 14, 21, and 28

2.6.3 *Subsidiary clinical outcomes*

- (i) Clinical status on day 7, 14, 21 and 28 according to the following ordinal scale:
 - a. All lesions completely resolved (all scabs dropped off and intact skin remains underneath, and all mucosal lesions healed)
 - b. Active lesions resolved (all skin lesions scabbed or desquamated, but not all completely resolved)
 - c. Active lesions persist but no new lesions in last 24 hours
 - d. New active lesion(s) in last 24 hours.
- (ii) Throat swab monkeypox DNA levels: monkeypox virus DNA concentration in throat swabs at Days 7, 14, 21, 28
- (iii) Number (%) of patients admitted to hospital for a complication of monkeypox (overall and by type)
- (iv) Time to sustained absence of use of analgesia for monkeypox symptoms, defined as time to consistently reporting no use of analgesia, up to 28 days after randomisation.

2.6.4 *Safety assessments*

- (i) Number (%) of patients suffering serious adverse events (overall and by type) within 28 days of randomisation
- (ii) Number (%) of patients suffering adverse events of special interest (overall and by type) within 28 days of randomisation. These are:
 - Vomiting
 - Diarrhoea
 - Fever
 - Severe tiredness
 - Swollen lymph glands
 - Headache

- Muscle or joint pain
 - Sore eyes
 - Shortness of breath
 - Secondary skin infection
 - Pain related to monkeypox symptoms
- (iii) Number (%) of patients suffering death, overall and by cause
- (iv) Reasons for prematurely stopping allocated study treatment

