Time to sustained absence of use of analgesia for monkeypox symptoms is defined as the first day from which analgesia is consistently not required until day 28. Imputation of missing data and the method of time-to-event analysis will be as for the primary outcome above.

4.1.4 *Safety outcomes*

The number and percentage of patients suffering suspected serious adverse reactions, suspected unexpected serious adverse reactions, and death (overall and by cause), will be listed by trial allocation. Adverse events of special interest (listed in 2.6.4) and reasons for study drug discontinuation, will be presented by randomised group as counts and percentages. Where possible, the absolute risk differences will be presented with confidence intervals, analysed using Fisher's exact test.

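### Seizure risk is the stated reason for excluding epilepsy, yet seizure is on neither special-interest list, and non-serious events off the SAP list reach no by-arm table

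*Protocol*

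**What the plan says.** **The exclusion.** Protocol 2.2.6 states: "The potential for tecovirimat to lower seizure threshold is unknown and so persons with a diagnosis of epilepsy will not be eligible for enrolment". The SAP repeats the criterion in 2.4.2 as "Diagnosis of epilepsy". Protocol Appendix 1, describing a Phase 3 study with 359 healthy adults in its safety evaluation, adds: "A total of 6 subjects discontinued drug due to mild adverse reactions and one abnormal EEG change".

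**What participants are asked.** The prompted terms in protocol 2.8(ii) are "headache, sore eyes, cough, shortness of breath, nausea, vomiting, diarrhoea, muscle aches, joint pain". They are introduced as examples, not as a complete list. Other non-serious events enter as new symptoms that the participant reports. The flowchart in protocol section 3 has a nurse or doctor call on days 7, 14, 21 and 28 and enquire about adverse events in general.

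**What is analysed.** SAP 2.6.4(ii) defines the outcome as "Number (%) of patients suffering adverse events of special interest (overall and by type) within 28 days of randomisation. These are", followed by a closed list of eleven terms. SAP 4.1.4 then says: "Adverse events of special interest (listed in 2.6.4) and reasons for study drug discontinuation, will be presented by randomised group as counts and percentages". For serious events, SAP 4.1.4 names suspected serious adverse reactions, suspected unexpected serious adverse reactions and deaths. SAP 2.6.4(i) lists serious adverse events overall and by type.

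**The concern.** The plan identifies one neurological risk as unresolved and restricts entry because of it, but does not name that event where safety is elicited or analysed. The setting makes this more than a formality. Treatment is taken at home with remote follow-up. Children from 13 kg may join, although protocol 2.2.4 says that the drug has not been studied in paediatric subjects in trials. Protocol 1.1 also gives encephalitis as a complication of mpox itself (under 1%), so a single seizure could come from the disease or the drug. The placebo group helps to separate the two only if both groups are asked in the same way and the counts are shown by arm.

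The reporting gap is wider than seizure. An event can be prompted for or volunteered, recorded and reviewed by medical staff, and still reach no randomised comparison because it is not on the SAP list.

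**Working it through.** The plan states no figure on this point, so the main check sets the text side by side. The arithmetic afterwards shows what a seizure count could and could not say.

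**1. The two lists**

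| | Protocol 2.8(ii) | SAP 2.6.4(ii) |
|---|---|---|
| Number of terms | 9 | 11 |
| In both | headache, sore eyes, shortness of breath, vomiting, diarrhoea, muscle aches, joint pain (7 terms) | the same, with muscle or joint pain as one term (6 terms) |
| In one only | cough, nausea (2) | fever, severe tiredness, swollen lymph glands, secondary skin infection, mpox-related pain (5) |
| Seizure, fit or blackout | no | no |

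Counts: 7 + 2 = 9 and 6 + 5 = 11. Nausea is prompted for but is not on the SAP list, although Appendix 1 names headache and nausea as the most frequent reactions (at least 5% of subjects).

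**2. Following a seizure through the plan**

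- Fatal, life-threatening, disabling, or needing inpatient admission: serious under protocol 2.8(i), and so within SAP 2.6.4(i). SAP 4.1.4 names it only if it is fatal or judged a suspected reaction.
- Not serious, but treatment stopped because of it: shown by arm among the stopping reasons (SAP 4.1.4).
- Not serious and treatment continued: protocol 2.8(i) has five criteria, none covering an event that is medically important on other grounds, so this is a non-serious event. It is not specifically asked about, is not on the SAP list, and has no by-arm output in protocol 2.4.4, SAP 2.6.4 or SAP 4.1.4.

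Only the third route is fully open. In the first, the analysis section needs to catch up with the outcome list.

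**3. What a complete seizure count could show**

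Inputs: 500 participants allocated 1:1 (protocol 2.6 and 3.4), so 250 per arm. With the protocol's allowance of about 10% losses, 250 × 0.9 = 225.

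Upper 95% bound (one-sided) with zero events, 1 − 0.05^(1/n):

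- n = 250: 1 − 0.05^(1/250) = 0.0119, about 1.2%
- n = 225: 1 − 0.05^(1/225) = 0.0132, about 1.3%

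Chance of at least one event among the treated, 1 − (1 − p)^n. The risks are assumptions, since the documents give no seizure risk:

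| Assumed risk | n = 250 | n = 225 |
|---|---|---|
| 1% | 92% | 90% |
| 0.4% | 63% | 59% |

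Fisher's exact test, two-sided, 250 per arm:

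- 5 v 0: 2 × (250·249·248·247·246)/(500·499·498·497·496) = 0.061
- 6 v 0: multiply by 245/495, giving 0.030

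Six treated-arm events against none would thus be needed for p below 0.05. The chance of six or more among 250 treated is about 4% at a true risk of 1% and 38% at 2%. A by-arm seizure count is descriptive.

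**The case against.** It can fairly be said that capture is broader than the lists. The protocol summary has all adverse events recorded and medically reviewed. Weekly calls enquire about adverse events. Participants complete a daily diary to day 28 and have a 24-hour line, and their own clinicians can report events. The DMC sees unblinded safety data. Excluding patients for an unknown risk is a precaution and does not oblige the trial to make that event an outcome. The case report forms, which SAP 5.1 says are published separately, were not available for this check and may contain further prompts.

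Much of this stands, and it rules out several stronger readings that a reader might infer:

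- *That nobody asks.* The text supports only that seizure is not specifically asked about.
- *That participants are out of contact between weekly calls.* The diary and telephone line contradict this.
- *That no seizure is compared by arm.* Seizures that are serious or that stop treatment fall within stated outcomes.
- *That the trial could settle the question behind the exclusion.* Those enrolled do not have a diagnosis of epilepsy, so even a complete count says nothing direct about people who do.
- *That Appendix 1 shows a seizure signal.* It reports one EEG change, not a seizure.

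What this does not close is the last step. The protocol list is open-ended but the SAP list is not, so a recorded seizure on the third route, or a recorded episode of nausea, has no place in the planned comparison even if both documents are followed exactly.

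**Conclusion.** The point holds as a gap in targeted ascertainment and in by-arm reporting. It covers a seizure that is neither serious nor a reason for stopping treatment, and every other recorded non-serious event outside the SAP list, with nausea and cough as the clearest examples. Separately, SAP 4.1.4 falls short of SAP 2.6.4(i) for serious events by type.

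The stakes are modest. Zero seizures under complete, prompted ascertainment would bound the risk at about 1.2% to 1.3% in people without epilepsy. Without a prompt, that bound depends on how fully general enquiry picks seizures up, which is unknown. These figures assume that the planned 500 are recruited and that losses are between none and 10% of the treated arm. The primary result does not change. Priority lies between an optional improvement and one that should be made: the seizure question is a sensible, cheap addition, and the reporting change has the stronger claim because it makes the analysis section cover what the trial already collects.

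**What to change.** - **Protocol 2.8(ii) and SAP 2.6.4(ii):** add seizure, fit or blackout to the prompted special-interest events, asked at the existing weekly calls.
- **Both lists:** reconcile them. Decide on cough and nausea (protocol only) and on fever, severe tiredness, swollen lymph glands, secondary skin infection and mpox-related pain (SAP only).
- **SAP 4.1.4:** state that all serious adverse events by type, and all recorded non-serious adverse events whether or not they are on the special-interest list, are tabulated by randomised group. State that seizure counts are descriptive, with an exact confidence interval for each arm.

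If the question is added after recruitment has begun, report how many participants in each arm were asked; the zero-event bound applies to them only. The new tabulation can cover everyone.

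The cost is one question, one entry in each list and one further table. No visit, sample-size or eligibility change is needed. The downside is that a few unrelated faints will be reported in both arms.
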